Upon arrival to the clinic on the day of the study visit, prior to the application of the reference and test devices, skin inspection of the application site will be conducted. The CPM Device will then be applied to the participant's chest as described in the IFU materials supplied with the device (the study team will also have received training on the proper placement of the device prior to the initiation of the study). This device will be worn for the entirety of the clinic visit (without removal and replacement). The reference device will also be used for each measurement taken during the visit, concurrently. On the CRF, the time that the CPM Device is placed on the chest will be denoted.

A Baseline measurement will then be initiated using the CPM Mobile Application in order to assign a system-generated patient ID to the participant as well as to establish the tilt angle for the following measurements. The first half of the measurement should be in the Fowler, sitting-upright position, and the second position should be in a Supine, lying-flat position. The reference device will also be used during this time to establish a respiration baseline.

The exercises below will then be followed, with the time of the start of each exercise recorded in the CRF. Four different versions of the exercises (Procedures A-D) will be available that differ only in the sequence of the measurements. The study staff will randomly select a procedure version, using the EDC. Only one procedure version per subject is used. The selected version for each subject will be recorded.

Each exercise will last approximately 4 minutes, or the time that it takes to complete one full measurement with the CPM device in measurement mode (initiated by the CPM mobile app). Within each measurement, participants will move through two positions, both upright and supine. Reference respiration data will be taken concurrently with the CPM device measurement. For each measurement, it is ensured that the reference device recordings are stabilized before initiating the CPM measurement sequence.

For items 1-17, capnography waveform and breath-by-breath reference tidal volume from a metabolic cart will be simultaneously recorded for comparison. For item 18, a diagnostic ECG and clinical grade temperature sensor data will be collected simultaneously.

<Procedure A>

Item	Respiration Rate	Tidal Volume	Mode	Duration
1	Natural (baseline)	Natural (baseline)	Doctor Setup, App	4 min

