Respiration Rate Accuracy

- 85% respiration rate error $\leq \pm 2$ BPM between reference and test device at 6-40 BPM

Relative Tidal Volume Relative Accuracy

- Root Mean Squared (RMS) of residual error after linear fitting $\leq 35\%$

Respiration Rate Endpoint Justification

The Respiration Rate is derived by the CP Analytics Engine from impedance measurements taken by the CPM device for a one (1) minute period. The CP Analytics Engine performs a quality control (QC) check for at least 30 seconds of consecutive impedance measurement samples. This QC-validated measurement data of at least 30 seconds results in a maximum computational accuracy of 2 BPM for the respiration rate. Consequently, an accuracy of 2 BPM is deemed sufficient for the CPM Device's intended use.

Relative Tidal Volume Endpoint Justification

Relative Tidal Volume as measured by an implanted device have shown to have day-to-day variability ranges between 10% and 14% in terms of coefficient of variation (Boehmer et al., *Journal of Cardiac Failure*, vol. 18, no. 8S, Aug, 2012). In addition, breath-to-breath tidal volume variability ranges from 18% to 43% depending on the underlying pulmonary disease conditions (Kuratomi et al. *Japanese Journal of Medicine*, vol. 24, no. 2, May, 1985), which further supports that day-to-day variability can be as high as 14%. Given this physiological day-to-day variability, it is considered that as high as 35% (about 2.58 times, $Z_{99.5\%}$, of 14%) of change can be

considered physiologic unless other clinical information strongly indicates otherwise. To correctly indicate the change greater than 35%, the relative error less than 35% is deemed sufficient to trend and indicate clinically significant change of rTV.

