Using the data that are classified by the CPM system as good quality, the percentage of the respiration rate whose error is within ± 2 brpm is derived. The confidence interval for the proportion of the errors within ± 2 brpm will also be characterized assuming that the number of data points whose errors are within ± 2 brpm follows binomial distribution.

Analysis 1-3: Respiration rate error limits of agreement

The limits of agreement will be derived using a conventional Bland-Altman analysis as well as non-parametric approach in case the distribution of the error has a long-tail, significant deviation of Normality assumption of the conventional Bland-Altman analysis.

The 85% limits of agreement (bias \pm 1.44 standard deviation) will be tabulated. The 95% confidence interval for the limits of agreement will also be derived. In case the kurtosis, calculated in the Analysis 1-1, is high indicating that the distribution of errors has a long tail, non-parametric limits of agreement will also be presented to correctly characterize the range which 85% of the errors are expected to be bounded by. The non-parametric 85% limits of agreement will also be derived based on 7.5% and 92.5% percentile of the errors. The 95% confidence interval for non-parametric limits of agreement will be derived using a bootstrap resampling method.

Analysis 1-4: Other respiration rate accuracy analyses

A 95% confidence interval (CI) for mean error (i.e., bias) will be tabulated. While the primary objective is to show that the CPM estimate is accurate within ± 2 brpm, the CI for mean error will additionally show if there is any systemic bias in the CPM estimate. The standard deviation of the paired differences will also be tabulated.

If the lower bound of the 95% confidence interval for the percentage of the errors within ± 2 bpm from Analysis 1-2 exceeds 85%, it is demonstrated with statistical significance that the CPM system's respiration rate accuracy is sufficient in comparison to the reference to support its intended use. Also, the other analyses should provide different lenses to characterize the respiration rate accuracy.

Analysis 2: Accuracy of relative changes of relative tidal volume

The primary objective of this analysis is to demonstrate the CPM system's relative tidal volume (rTV) is accurately tracking true changes in tidal volume (TV).

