For each subject, relative tidal volume from the CPM system and the tidal volume from the reference device under the breathing-depth controlled condition (natural ~ 500 mL, shallow ~ 250 mL, deep ~ 750 mL, very deep >1 L) and the breathing-rate controlled condition (e.g., 10, 15, 25, 30 bpm) will be compared for each body posture. A scatter plot of relative tidal volume produced by the CPM system and the tidal volume measured by the reference device will be produced. Each graph will be summarized by two least-squares linear regression fits. One is produced in a linear scale and the other is produced in a log scale to characterize the relative accuracy.

Analysis 2-1: Respiration rate error descriptive statistics

The descriptive statistics includes but not limited to:

- Percentage of the CPM system's rTV estimate not reported due to bad signal quality.
- Mean, median, variance, standard deviation, skewness, kurtosis, root mean squared error, and root median squared error.

Analysis 2-2: Least-squares linear regression analysis in rTV and TV

The accuracy of relative changes of rTV will be summarized by Pearson correlation coefficients across subjects. Then, mean correlations will be determined using Fisher's z-transformation to combine the subject specific coefficients and then back transformed. A 95% confidence interval on mean correlation coefficient will also be derived.

Analysis 2-3: Least-squares linear regression analysis in natural logs of rTV and TV

The accuracy of relative changes of rTV will be summarized by Pearson correlation coefficients across subjects obtained using natural logs of rTV and TV. Then, mean correlations will be determined using Fisher's z-transformation to combine the subject specific coefficients and then back transformed. A 95% confidence interval on mean correlation will also be derived.

After the linear fit, root mean square of the relative residual errors will also be characterized. A 95% confidence interval on the root mean squared relative errors will also be derived using Chi-squared distribution assuming the relative residual errors follows a zero-mean Gaussian distribution.

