If the root mean square of the relative errors from Analysis 2-3 and its confidence interval does not exceed 35% per end-point in the protocol (CEPR0002), it is demonstrated that the CPM system's relative tidal volume is sufficiently accurate in following relative changes in comparison to the reference. Mean correlation coefficients from Analysis 2-2 and 2-3 will also support that the primary objective of this Analysis 2 is achieved.

Analysis 3: ECG and Skin Temperature Capabilities

The primary objective of this analysis is to evaluate the secondary objectives regarding the ECG and skin temperature capabilities of the CPM system. For skin temperature, the descriptive analyses will be performed in comparison the reference measurement For ECG capabilities, if the data is available, the quality of the CPM ECG can be evaluated.

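### The rTV success rule rests on residual RMS alone, so it cannot fail a device for moving opposite to tidal volume; the degrees of freedom behind its 35% limit are also unstated

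*SAP*

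**What the plan says.** - **Decision rule (SAP, end of Analysis 2).** The condition is "If the root mean square of the relative errors from Analysis 2-3 and its confidence interval does not exceed 35" per cent. If it is met, rTV is declared sufficiently accurate in following relative changes. On correlation the SAP adds "Mean correlation coefficients from Analysis 2-2 and 2-3 will also support" the objective, and gives no value to be reached.
- **The fit (SAP, Analysis 2 and 2-3).** "Each graph will be summarized by two least-squares linear regression fits", one linear and one in logs; the rule uses the log fit. No slope constraint is mentioned and the response variable is not named. Fisher's z is used "to combine the subject specific coefficients and then back transformed", which points to fits within subject.
- **The interval (SAP, Analysis 2-3).** The limits for the RMS are "derived using Chi-squared distribution assuming the relative residual errors follows a zero-mean Gaussian distribution". The degrees of freedom are not given, and the relative residual is not defined.
- **Posture.** Protocol, Study Procedures: "Within each measurement, participants will move through two positions, both upright and supine". The SAP makes the comparison separately by posture, but does not say how the two postures enter the single RMS.
- **Endpoint (Protocol).** Primary Outcome Measures list both the residual RMS and the within-subject correlation. The Endpoints section sets a limit only for the RMS. The reason given for it is that "the relative error less than 35% is deemed sufficient to trend and indicate clinically significant change of rTV".

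**The concern.** The objective is that rTV tracks true changes in tidal volume (TV). Tracking has a direction and a size. Residual scatter about a freely fitted line measures neither; it measures only how tightly the points lie around whatever line was fitted. A rule built on that alone can declare tracking demonstrated for a device whose readings move the wrong way or, depending on the response variable, do not move with TV at all.

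The unstated degrees of freedom raise a second problem. With two parameters fitted to every short line, dividing by the number of readings or by the residual degrees of freedom gives clearly different RMS values and limits. If this is left open, the verdict on a primary objective could be chosen after the data are seen.

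**Working it through.** **Inputs.** From the documents: limit 35%; prior RMS 25.2–30.4%; 8 readings per subject; 40 subjects, up to 60; two postures; nominal volumes 250, 500, 750 and 1000 mL, plus four rate-controlled readings at natural depth. Assumed: those four at 500 mL, 10% jitter in achieved volume, independent Gaussian log errors, two-sided 95% limits.

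**0. The plan's own figure.** Protocol, Sample Size Justification, gives 136 readings for 95% power. A one-sample chi-square variance test at 30.4% against 35% needs 274–276 readings one-sided (331–333 two-sided). At 136 the power is 73% or 61%. The figure is not reproduced. That is a separate matter, and nothing below depends on it.

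**1. Direction.** For a least-squares line, residual SS = Syy(1 − r²). Replacing ln rTV by −ln rTV changes r to −r and leaves r², the RMS and its interval unchanged, whichever variable is the response. On log residuals this is exact.

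**2. Pass rate, ln rTV as response.** One 8-point line per subject gives N = 320 and residual df = 320 − 2×40 = 240. Residual SS/σ² is chi-square with 240 df at any slope, so

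P(pass) = P(χ²₂₄₀ ≤ χ²₀.₀₂₅,₂₄₀ × (0.35/σ)²), with χ²₀.₀₂₅,₂₄₀ ≈ 199.0.

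At σ = 0.30: 199.0 × 1.361 = 270.8, giving about 92%. Simulation agrees: the inverse device (log slope −1, mean r about −0.84) and the flat device (slope 0) each pass about 90–92%, like a correct device with the same noise.

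**3. Sensitivity.**
- If the relative residual is exp(e) − 1, the inverse and flat devices each pass about 50%.
- If ln TV is the response, the inverse device passes 100% and the flat device about 0% at nominal volumes.

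**4. Degrees of freedom.** At a true residual SD of exactly 0.35, with k df used in the interval, P(pass) = P(χ²_df ≤ χ²₀.₀₂₅,k).

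| Lines | N | Residual df | k = residual df | k = N |
|---|---|---|---|---|
| One 8-point line per subject | 320 | 240 | 2.5% | 92.6% |
| One line per subject and posture | 640 | 480 | 2.5% | 99.8% |

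Take the protocol's 30.4%, if it was computed with divisor N on 8-point lines: SS = 0.304² × 320 = 29.57. The upper limit is √(29.57/272.3) = 33.0% with N df (pass) and √(29.57/199.0) = 38.6% with residual df (fail). The protocol does not say which divisor it used.

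**5. Posture.** Suppose the observed RMS is 25% upright and 39% supine, with equal df. Pooled RMS = √((0.0625 + 0.1521)/2) = 32.8%. With 480 df the upper limit is 32.8% × √(480/421.2) = 34.97%. The pooled rule passes although supine alone is above 35%.

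**6. Adding a correlation condition (lower 95% limit above 0).** In the step 2 setting, the inverse device falls to 0% and the flat device to about 2%. A slope-1 device with 30.4% error passes 86% with and without it.

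**The case against.** The strongest reply is that a reversed device is hypothetical and could not go unnoticed. The protocol derives rTV from impedance changes caused by breathing, and nothing in the documents suggests that it falls as breaths deepen. The SAP also requires scatter plots and signed mean correlations with 95% intervals, and a mean correlation near −0.8 could hardly support the objective. This stands as far as visibility goes: the gap is an unformalised criterion, not a hidden result. It does not repair the rule, which would still declare success and would need someone to override it. The flat-device case needs no reversal.

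A reader might infer more than the documents support:

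- *That no reversed device can ever fail.* It can fail on scatter, as a correct one can; only its direction is ignored.
- *That the SAP uses N degrees of freedom.* It states none. The 92.6% and 99.8% are conditional on that reading and on within-subject fits.
- *That posture is ignored.* The SAP compares by posture; only the rule for combining the two is missing.
- *That a correlation condition makes the endpoint a test of the size of change.* It does not. At log slope 0.3, a 35% rise in TV shows as 1.35^0.3 − 1 = 9.4%. With 20% noise and ln rTV as response, such a device still passes 100% with the condition added.

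**Conclusion.** The concern holds in this limited form. The sign-blindness is exact for log residuals and needs no assumption about the data beyond an unconstrained slope, which is inferred from the plain least-squares wording. The pass rates are illustrative. They rest on nominal volumes, independent Gaussian errors, 40 subjects and 8-point lines, and they fall to about 50% if residuals are back-transformed. That a device unrelated to TV passes depends on ln rTV being the response.

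The direction gap should be fixed; it is not fatal, because the reported correlation would expose the problem. The degrees of freedom must be settled before the data are analysed, because the choice alone can turn a fail into a pass at the limit and at the protocol's own prior figure.

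**What to change.** **(a) Decision rule.** Keep the 35% RMS endpoint. Also require the lower 95% limit of the Fisher-z mean within-subject log correlation to exceed 0, with one coefficient per subject (average the two posture z values). The sponsor may pre-specify a higher value from its prior data.

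**(b) Analysis 2-3.** Compute RMS as √(residual SS / (N − 2 per fitted line)) and use the same df in the chi-square limits. Define the relative residual as the log-scale residual. This matters for a good device too: with exp(e) − 1, a slope-1 device with 30.4% error and 8-point lines drops from 86% to about 40%. Name the response variable. State whether 35% applies to the pooled RMS or to each posture.

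**(c) Supportive.** Report the mean log slope with its 95% interval, since (a) does not exclude a damped device.

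**Cost.** SAP wording and a few lines of code; no new data. There is a second pass condition. RMS rises by 1/√(6/8) − 1, about 15% in relative terms, for 8-point lines. At 30.4% error with 40 subjects and one 8-point line each, power is 86% with a two-sided 95% limit or 92% at one-sided 0.05, against the stated 95%. Reaching 95% takes 56 or 46 subjects respectively, within the ceiling of 60. With one line per subject and posture and a pooled RMS, 40 subjects give 99% (two-sided limit). The sponsor should check which divisor produced its 30.4%: if it was N on 8-point lines, the same data give 30.4% × 1.155 = 35.1% with residual df, and such a device would fail.

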IRB Minimal Risk Protocol Template

Note: If this study establishes a human specimen repository (biobank) for research purposes, do not use this template. Use the Mayo Clinic Human Specimen Repository Protocol Template found on the IRB home page under Forms and Procedures at <http://intranet.mayo.edu/charlie/irb/>

First-time Use: Use this template to describe your study for a new IRB submission.

1. Complete the questions that apply to your study.
2. Save an electronic copy of this protocol for future revisions.
3. When completing your IRBe application, you will be asked to upload this document to the protocol section.

Modification: To modify this document after your study has been approved:

1. Open your study in IRBe. Click on the study 'Documents' tab and select the most recent version of the protocol. Save it to your files.
2. Open the saved document and activate "Track Changes".
3. Revise the protocol template to reflect the modification points, save the template to your files
4. Create an IRBe Modification for the study and upload the revised protocol template.

General Study Information

Principal Investigator: [name]

Study Title: Clinical Validation Study for Noninvasive Cardiopulmonary Management Device (Phase II)

Sponsor: Analog Devices, Inc.

Clinical Research Organization: N/A

Protocol version number and date: 1.0 – February 7, 2022

Research Question and Aims

Hypothesis:

It is hypothesized that the ADI CPM System (test device) will be able to measure in healthy human volunteers:

- a) Respiration Rate (RR) with sufficient accuracy
- b) Changes in relative Tidal Volume (rTV) with sufficient accuracy

Objectives:

Primary Objectives

- 1) Validate Respiration Rate (RR) accuracy derived by the Cardiopulmonary Management (CPM) System in the range of 6-40 BPM
- 2) Validate relative changes in relative Tidal Volume (rTV) derived by the CPM System

*Secondary Objectives**

- 1) Confirm the ECG capabilities of the CPM System
- 2) Confirm the Skin temperature capability of the CPM system

Outcome Measures:

Primary Outcome Measures

- 1) Accuracy of CPM System calculated RR versus reference device
 - Proportion of the error within ± 2 bpm
- 2) Accuracy of the changes in the rTV calculated by CPM System compared to reference TV
 - Root Mean Squared (RMS) of residual relative error after linear fitting.
 - Correlation coefficient between reference device's TV and test device's rTV within subjects

*Secondary Outcome Measures**

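### The relative tidal volume success rule puts no estimate, interval or limit on the log-log slope, so a pass does not show that changes are reported at their true size

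*SAP*

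**What the plan says.** The protocol's second primary objective is to "Validate relative changes in relative Tidal Volume (rTV) derived by the CPM System". Its Endpoints section requires the RMS of the residual error after linear fitting to be at most 35%. The Relative Tidal Volume Endpoint Justification gives the reason for that limit: "To correctly indicate the change greater than 35%, the relative error less than 35% is deemed sufficient to trend and indicate clinically significant change".

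In the SAP, Analysis 2-3 is titled "Least-squares linear regression analysis in natural logs of rTV and TV". It takes Pearson correlations per subject, averages them through Fisher's z, and adds: "After the linear fit, root mean square of the relative residual errors will also be characterized". The decision rule that follows declares that the device's "relative tidal volume is sufficiently accurate in following relative changes in comparison to the reference" on this condition: "If the root mean square of the relative errors from Analysis 2-3 and its confidence interval does not exceed 35" per cent. The correlations have a supporting part: "Mean correlation coefficients from Analysis 2-2 and 2-3 will also support that the primary objective of this Analysis 2 is achieved". They have no threshold.

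Analysis 2 also plans scatter plots with fitted lines on the linear and log scales. Neither document says which variable is the response, which divisor the RMS uses, what slope is expected, or what slope would be unacceptable.

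**The concern.** The objective and the conclusion are about relative changes. Write ln(rTV) = a + b·ln(TV) + error. The intercept a carries the arbitrary units of rTV and is rightly removed. The slope b is not a nuisance: if true volume changes by a ratio R, the device reports a ratio R^b. Slope 1 reports changes at true size, a slope below 1 compresses them and a slope above 1 expands them. Residuals are taken after both a and b have been fitted to the subject's own reference data, so the deciding statistic does not measure the departure of b from 1.

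The protocol justifies 35% by the need to indicate changes above 35% correctly, and that depends on b. A compressed scale would hide real changes and an expanded one would create apparent ones. The intended use is spot checking, including at home, and the plan describes no reference reading there from which a patient's scale could be corrected.

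**Working it through.** **Inputs from the documents.** Eight rTV readings per subject (protocol, Sample Size Justification): depth targets of about 250, 500, 750 and 1000 mL, plus four rate-controlled readings at natural volume. Two postures per reading; 40 subjects; limit 35%; prior residual RMS 25.2–30.4%.

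**Assumptions.** The four rate-controlled readings are at 500 mL. There is one line per subject and posture. Scatter is Gaussian on the log scale and is placed on rTV. The upper confidence limit is the SAP's chi-squared limit, two-sided 95%. Scatter is varied from 10% to 30.4%.

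**The plan's own figure.** 2.58 × 14% = 36.1%, which the protocol gives as about 35%. The rounding does not affect this point.

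**1. What the slope does to a reported change.** Reported change = R^b − 1.
- b = 0.5: 1.35^0.5 − 1 = +16%. To show +35%, TV must rise by 1.35^2 − 1 = 82%. A doubling reads as 2^0.5 − 1 = +41%, and a halving as 0.5^0.5 − 1 = −29%.
- b = 2: a true +35% reads as 1.35^2 − 1 = +82%. The device shows +35% after a rise of 1.35^0.5 − 1 = 16%.

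**2. What the rule sees without noise.** For b = 0.5 or 2 the log-log residuals are zero and the log-scale correlation is 1. The sum of squares of ln(TV) over the eight targets is Sxx = 1.105. If b were held at 1 and only the intercept removed, the RMS error would be |b − 1|·√(1.105/8): 0.5 × 0.372 = 18.6% for b = 0.5, and 1 × 0.372 = 37.2% for b = 2. A 35% limit on that quantity would catch b = 2 but not b = 0.5, so the slope has to be looked at directly.

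**3. What the rule sees with noise.** Simulation of 40 subjects × 2 postures × 8 readings, with RMS on divisor n − 2 per line. Entries are RMS, with the share of runs that pass where it is below 99%.

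| Response | Scatter | b = 0.5 | b = 1 | b = 2 |
|---|---|---|---|---|
| ln rTV | 10% | 10% | 10% | 10% |
| ln rTV | 25.2% | 25% | 25% | 25% |
| ln rTV | 30.4% | 30% | 30% | 30% |
| ln TV | 10% | 18% | 10% | 5% |
| ln TV | 25.2% | 32% (78% pass) | 22% | 12% |
| ln TV | 30.4% | 34% (about 2% pass) | 25% | 14% |

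If true TV also varies by 10% around its target, the two penalised cells become about 52% and under 1%. With divisor n instead of n − 2, slope 0.5 passes in both. Slope 0, meaning no tracking at all, passes with rTV as response and fails with TV as response.

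**4. What the correlations add.** At a given residual sum of squares SSE, r² = b²·Sxx/(b²·Sxx + SSE). With 30% scatter SSE is about 6 × 0.09 = 0.54. For b = 0.5, r² = 0.276/0.816 = 0.34, so r is about 0.58; b = 1 gives about 0.82 and b = 2 about 0.94. The simulated Fisher-z means are close:

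| Scatter | b = 0.5 | b = 1 | b = 2 |
|---|---|---|---|
| 10% | 0.92 | 0.98 | 0.99 |
| 25.2% | 0.67 | 0.88 | 0.97 |
| 30.4% | 0.60 | 0.84 | 0.95 |

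Compression lowers r and expansion raises it. With no threshold, neither affects the decision.

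**5. Precision of a slope estimate.** The 95% half-width of the mean slope over 40 subjects, averaging two postures, is 2.02·√[(τ² + s²/(2 × 1.105))/40]. With s = 0.30 it is 0.06 if slopes are equal (τ = 0), and 0.12 if they vary between subjects with SD τ = 0.3 (an assumption).

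**The case against.** Several stronger readings are tempting, and the documents do not support them.

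- A reader might infer that a device reading half or double the true volume would pass wrongly. A pure gain is not an error: rTV has relative units, and a gain leaves the log-log slope at 1.
- A reader might infer that a wrong slope passes with almost no error and almost perfect correlation. That describes only a nearly noise-free device. At the documented 25–30% scatter and slope 0.5, r is about 0.6–0.7.
- A reader might infer that the correlations carry no information on the slope. They do: RMS and r together, with the spread of reference TV, imply it. But r has no threshold, and expansion makes it look better.
- A reader might infer that the rule passes any slope. With TV as response and divisor n − 2, slope 0.5 mostly fails at 30% scatter. The SAP states neither the direction nor the divisor, and slope 2 passes either way.
- A reader might infer that slopes will not be seen. The fitted lines are planned output, and the descriptive list in Analysis 2-1 is open-ended. What is missing is a named estimate, its interval and a role in the conclusion.
- A reader might infer that this device compresses changes, for example through an additive impedance artefact. Nothing in the documents indicates this.

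It is also fair to object to a fixed pass band for the slope. The protocol defines the endpoint as RMS after fitting, and the documents give no basis for a particular band. Error in the reference TV also pulls the slope down: with an assumed 10–15% error, a perfect device averages about 0.96–0.90. With a half-width of 0.12 its lower limit would be about 0.84–0.78, so it could miss a lower bound of 0.8.

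**Conclusion.** The concern holds in this form: the stated rule can declare relative changes accurate without any check that they are reported at true size. The change formula and the noise-free result are exact. The pass rates and correlations rest on the target volumes, Gaussian log-scale scatter on rTV and one line per subject and posture. With rTV as response the outcome does not depend on the slope between 0 and 2. With TV as response the rule penalises compression at the documented scatter and rewards expansion. Neither version tests what the 35% justification needs. This does not show that the device's slope is wrong, only that a pass could not rule that out.

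**What to change.** In Analysis 2-3:
- State the regression direction (ln rTV on ln TV) and the RMS divisor.
- Report the mean within-subject log-log slope, averaged over the two postures, with a 95% CI across subjects and its range.
- Tabulate device and reference percent change from the subject's natural-depth reading for the shallow, deep and very deep items.

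In the Analysis 2 decision paragraph, word the conclusion to match. Claim accuracy for the size of relative changes only if the slope interval supports it against a margin that the sponsor justifies before analysis, allowing for attenuation from error in reference TV. Otherwise limit the claim to tracking changes up to an unknown scale factor on the log scale. A band such as 0.8–1.25 is only an illustration.

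The estimates come from fits already planned, so no new data are needed. The cost is SAP wording, a margin to justify, and a possibly narrower claim. If the slope is made a formal condition for success, the protocol's endpoint wording should be aligned as well.
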